3.4.9 Prior medications vs. concomitant medications

Medications will be classified as follows:

- Prior medications are those the participant used prior to first dose study drug. Prior medications can be discontinued before first dose of study drug or can be ongoing during treatment period.
- Concomitant medications are any interventions received by the patient concomitantly to study drug during the on-treatment period, i.e., from date of first dose of study drug to the date of last dose of study drug +1.
 - Per protocol patients are not allowed to initiate new ITP medication after 1st dose of study drug unless it is a rescue medication. Thus, concomitant non-rescue ITP medication would include ITP medication started prior to the 1st dose and ongoing up to the date of last dose of study drug +1 only.
- Post-treatment medications are those the patient took in the period running from the end of the concomitant medications period up to the end of the study.

A given medication can be classified as a prior medication and/or as a concomitant medication and/or as post-treatment medication. If it cannot be determined whether a given medication was taken prior or concomitantly or post, it will be considered as prior, concomitant, and post-treatment medication.

3.4.10 Study Day

The date of first study drug dosing is considered as Study Day 1.

- Study Day = (Date of assessment date of first dose + 1), if the assessment date is on or after the date of first dose.
- Study Day = (Date of assessment date of first dose), if the assessment date is prior to the date of first dose.

3.4.11 Completed 24 Weeks of Main Treatment

Completed 24 weeks of main treatment = (Date of last dose in main study – Date of first dose + 1) \geq 165 days, taking into consideration of +/- 3 days visit window

3.4.12 Duration of ITP (primary or secondary) (years)

Duration of disease (years) = ((Date of first study drug dosing – Date patient was diagnosed with ITP+ $\frac{1}{30.4375}$)/12

3.4.13 Time since Most recent prior therapy/Splenectomy (months)

Time since event (months) = (Date of first study drug dosing – Date of event + 1)/30.4375. For patients who are still on their most recent therapy, this will equal 0.

3.5 Data Handling

3.5.1 Partial dates

For the purpose of categorizing treatment emergent events or mediation period, imputation of day, month and/or year for partial or missing AE onset dates or medication start date will be performed as described below.

- Day, month and year missing
 - Leave as missing, no imputation. In this case, the adverse event will be considered as treatment emergent.
- Day and month missing
 - If year of start date is prior to the year of the 1st dose of rilzabrutinib, then impute day and month as 31-DEC, ELSE
 - If year of start date is the same as the year of the 1st dose of rilzabrutinib, then impute day and month as the day and month of 1st dose of rilzabrutinib, ELSE
 - If year of start date is after the year of the 1st dose of rilzabrutinib, then impute day and month as 01-JAN (Note that this situation is rare, and the sponsor will make every effort to obtain the actual month that the AE started.)
- Only day missing
 - If month and year of start date are prior to the month and year of the 1st dose of rilzabrutinib, then impute day as the last day of the month, ELSE
 - If month and year of start date are the same as the month and year of the 1st dose of rilzabrutinib, then impute day as day of 1st dose of rilzabrutinib, ELSE

- If month and year of start date are after the month and year of the 1st dose of rilzabrutinib, then impute day as 01.

Imputation of day, month and/or year for partial or missing medication stop dates will be performed as described below if the medication is not flagged as "Ongoing". If the imputed start date is after the imputed end date, then the imputed start date will be set to be the same as the imputed stop date.

- Day, month and year missing
 - Leave as missing, no imputation. In this case, the medication will be considered as concomitant.
- Day and month missing
 - If year of stop date is prior to the year of the 1st dose of rilzabrutinib, then impute day and month as the last day of the last month
 - If year of stop date is the same as the year of the 1st dose of rilzabrutinib, then impute day and month as the date prior to the day and month of 1st dose of rilzabrutinib,
- Only day missing
 - If month and year of stop date are prior to the month and year of the 1st dose of rilzabrutinib, then impute day as the last day of the month, ELSE
 - If month and year of stop date are the same as the month and year of the 1st dose of rilzabrutinib, then impute day as the date prior to the day of 1st dose of rilzabrutinib.
 - If month and year of stop date are after the month and year of the 1st dose of rilzabrutinib, then impute day as 01.

Imputation of day and month for other imprecise date such as Date of Diagnosis will be performed as described below.

- If only day is missing, impute as 01
- If day and month are missing, impute as 01-JUL

The imputation of missing or partial dates are for categorization purpose only and will not be used in the listings.

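### SAP Part A 3.5.1 sets partial medication stop dates in the month or year of first dose to the day before dosing, so drugs possibly used on treatment are classed as prior only

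*SAP*

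**What the plan says.** SAP Part A 3.5.1 gives the date rules and states their purpose: "For the purpose of categorizing treatment emergent events or mediation period". Stop-date imputation "will be performed as described below if the medication is not flagged as" ongoing. The parts that matter here are:

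- **Stop, day missing, month and year of first dose:** "then impute day as the date prior to the day of 1st dose of rilzabrutinib".
- **Stop, day and month missing, year of first dose:** "impute day and month as the date prior to the day and month of 1st dose of rilzabrutinib".
- **Stop, day missing, a later month:** day 01 of that month.
- **Stop, year only, a year after first dose:** no rule.
- **Stop completely missing:** "Leave as missing, no imputation. In this case, the medication will be considered as concomitant".
- **Start, day missing, month and year of first dose:** "then impute day as day of 1st dose of rilzabrutinib, ELSE". A year-only start in the first-dose year is also set to the first-dose date.
- **Imputed start later than imputed stop:** "then the imputed start date will be set to be the same as the imputed stop date".

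Section 3.4.9 defines the prior, concomitant and post-treatment periods. For a drug whose timing cannot be determined, it says "it will be considered as prior, concomitant, and post-treatment medication".

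**The concern.** A stop date known only to the month or year of first dose usually leaves open whether the drug was still in use after dosing began. Section 3.5.1 settles every such case as stopped before dosing. A record with no stop date at all is kept as concomitant. Adding a month or year that does not rule out on-treatment use therefore removes the drug from the concomitant set.

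The classification feeds several Part A outputs:

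- the concomitant-medication tables by dose level (5.1.5);
- the monotherapy and concomitant-ITP subsets of the primary endpoint (5.4.1.1, items 6 and 7);
- the table of treatment-emergent adverse events by concomitant ITP medication (5.5.1).

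A patient whose only background ITP drug is reclassified could appear as a monotherapy patient.

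**Working it through.** The plan gives no figure to reproduce. The check applies the 3.5.1 rules literally to example records and classifies the results by 3.4.9. The dates are assumed: first dose 11-Mar-2019, and last dose on treatment day 168, which is 25-Aug-2019.

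| Recorded start | Recorded stop | Dates after 3.5.1 | Result |
|---|---|---|---|
| 01-Jun-2018 | Mar-2019 | 01-Jun-2018 to 10-Mar-2019 | prior only |
| 01-Jun-2018 | 2019 | 01-Jun-2018 to 10-Mar-2019 | prior only |
| Mar-2019 | Mar-2019 | start 11-Mar moved to 10-Mar; stop 10-Mar | prior only |
| 2019 | 2019 | start 11-Mar moved to 10-Mar; stop 10-Mar | prior only |
| 20-Mar-2019 | Mar-2019 | 20-Mar to 10-Mar | stop before start |
| 20-May-2019 | 2019 | 20-May to 10-Mar | stop before start |
| 20-May-2019 | May-2019 | 20-May to 01-May | stop before start, still on treatment |
| 01-Jun-2018 | 2020 | none | no rule |

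Three further cases:

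- **First dose on the 1st.** With first dose 01-Mar-2019 and stop Mar-2019, the imputed stop is 28-Feb-2019. This lies outside the recorded month, yet every possible stop date is on or after first dose.
- **Later month and dose level.** A patient who starts on 11-Mar and escalates after 28 days reaches the next level on 08-Apr. A stop recorded as Apr-2019 becomes 01-Apr, so any use at the second level is lost from the by-dose table.
- **Same record, stop blank.** With start 01-Jun-2018 and no stop date, 3.5.1 gives concomitant and 3.4.9 gives all three periods. Neither gives prior only.

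**Share of such stops truly on or after first dose.** Assume a month or year of L days, first dose on day d, and the true stop day uniform over the L days. Then

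share = (L − d + 1) / L, and its mean over d = 1 to L is (L + 1) / (2L).

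- Month, L = 30: d = 1 gives 30/30 = 100%; d = 15 gives 16/30 = 53%; d = 30 gives 1/30 = 3%. The mean is 31/60 = 52%.
- Year, L = 365: d = 1 gives 100%; d = 183 gives 183/365 = 50%; d = 365 gives 1/365 = 0.3%. The mean is 366/730 = 50%.

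**Effect on the concomitant-ITP subsets.** Section 3.4.9 describes a concomitant non-rescue ITP drug as one begun before first dose and still in use up to the day after last dose. Read strictly, a drug stopped in the first-dose month seldom qualifies, whatever day is imputed. A year-only stop can still qualify. In the example, stops from 26-Aug to 31-Dec would do so: 6 + 30 + 31 + 30 + 31 = 128 of 365 days, or 35%. The rule makes all of them prior only.

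**The case against.** The strongest defence is that 3.5.1 exists to determine timing, and that the 3.4.9 default covers only what remains undetermined after imputation. On that reading the two sections coexist. This is a fair reading of 3.4.9, but it does not explain why 3.5.1 treats a blank stop as concomitant and a partly known one as prior only. It also does not remove the impossible dates.

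A reader might infer more than the documents support:

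- **That the primary endpoint is affected through its four-week rescue clause.** Section 3.5.1 says that imputed dates serve only to assign categories and stay out of the listings. Under 5.4, rescue in Part A leads to discontinuation, and response is judged on counts taken before the rescue. Nothing shows that an imputed stop date enters that clause.
- **That the rule consistently favours rilzabrutinib.** Moving a patient from the concomitant to the monotherapy subset leaves the overall rate unchanged and can raise or lower either subset. These subsets are descriptive and no hypothesis is tested. If imputed stops did enter the rescue look-back, a rescue drug stopped months before dosing would move to the day before first dose and could block early responses.
- **That rescue drugs given on study become prior only.** This needs a partial start as well, and rescue status taken from dates. The SAP does not say whether status comes from dates or from an eCRF flag. With a known on-study start, the defect is a stop before the start.

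Three limits also stand. Records flagged as ongoing are exempt. Permitted steroids and TPO receptor agonists are meant to stay at a fixed dose (Protocol 4.12.1), so many will run past the first-dose month. Medications are reviewed at clinic visits twice per cycle, so partial dates may lie mainly in older, pre-study drugs.

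**Conclusion.** The rule is wrong as written, within a limited scope. For partial stops in the first-dose month or year, records with a pre-dose or partial start become prior only, even though use on treatment is possible. This is inconsistent with 3.5.1's own handling of a missing stop and with the 3.4.9 default. The rule can also place a stop outside its recorded month or before a known start. In later months, day 01 can do the latter and can drop a dose level.

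The outputs clearly exposed are the concomitant-medication tables in 5.1.5. The subsets in 5.4.1.1 items 6 and 7 and the adverse-event table by concomitant ITP medication are possibly exposed, mainly through year-only stops. An effect on the rescue tables is conditional, as described above.

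The averages of about 52% (month) and 50% (year) rest on assumed uniform stop days and first-dose days. They describe the share of affected records, not of all medication records. The documents do not give the number of partial dates, so the effect on any table cannot be sized and may be nil.

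**What to change.** Replace the stop-date rules in 3.5.1 with one of two options, and state which:

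1. Impute a partial stop to the latest date compatible with the recorded month or year, capped at end of participation and never before a known start. In the example, a stop of Mar-2019 becomes 31-Mar-2019 and the drug is prior and concomitant. A pair of dates both recorded as Mar-2019 no longer triggers the move of the start date.
2. Leave the stop unimputed whenever the recorded month or year allows use on or after first dose, and apply the 3.4.9 default.

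Under either option, add a rule for year-only stops in years after first dose. Make the completely missing stop consistent between 3.5.1 and 3.4.9. State whether rescue status is taken from dates or from the eCRF.

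The text change is a few lines. The Part B SAP (1.1) says that a Part A study report has been prepared, so the practical step is to count the affected records. If there are none, one sentence closes the point. Otherwise, rerun the medication tables and any subset or adverse-event table in which a patient changes category.

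The downside is that some drugs truly stopped before first dose will count as concomitant. This is most marked for year-only stops: a drug stopped in January would be carried past a March first dose. Option 2 has the further cost of counting some drugs as post-treatment when the recorded month excludes it.

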3.5.2 Missing data imputation

An unscheduled platelet count will be allocated to the scheduled visit if it is within the visit window of the scheduled visit with missing platelet count.

Other missing data will not be imputed.

3.5.3 Lab values below or above a threshold

For quantitative analyses, Lab values below the lower limit of quantitation/detection limit (LLOQ) will be replaced by half of the LLOQ, data above the upper limit of quantification will be replaced by ULOQ value.

3.6 Interim Analyses

No interim analysis is planned.

3.7 Handling of Study Center Effects

Study center effects will not be assessed.

3.8 Documentation & Other Considerations

Data are entered electronically into a clinical database built by Medidata RAVE and exported as SAS® datasets. SDTM and ADaM datasets will be generated following the Clinical Data Interchange Standards consortium (CDISC) conventions (SDTMIG v3.2 and ADaMIG v1.1). Summary tables and figures will be produced based on the ADaM datasets and patient data listings will be produced based on the SDTM datasets or raw clinical database. All tables, figures and listings will be produced using SAS® version 9.4.

Medical conditions and AEs are coded using the Medical Dictionary for Regulatory Activities (MedDRA) version 20.1, to assign a primary system organ class (SOC) and preferred term (PT) to each AE. Prior and concomitant medications are coded to preferred drug names using the World Health Organization Drug Dictionary (WHODRUG) version (WHO-DDE) B2, September 2017.

Continuous data will be summarized with the following descriptive statistics unless otherwise noted: number of observations, mean, standard deviation (SD), median, minimum, and maximum. Categorical data will be summarized with frequencies and percentages.

No hypothesis testing will be performed. P-values may be generated for exploratory purpose.

For presentation of continuous data, the mean, median, SD and LS mean will be presented to 1 decimal place greater than the original data and the minimum and maximum will have the same number of decimal places as the original data. The format for minimum and maximum will be "Min, Max". Standard deviation will be abbreviated as "SD" and standard error will be abbreviated as "SE". For presentation of categorical data, percentage will be reported to 1 decimal place. Confidence Intervals (CI), difference in percentage and CI will be reported to 2 decimal places.

3.9 Data base lock

The database is planned to be locked approximately 4-6 weeks after all patients have completed or discontinued the main study period.

4 STATISTICAL METHODS

4.1 Primary Efficacy Endpoints

The primary efficacy endpoint is:

 Proportion of patients able to achieve two or more consecutive platelet counts, separated by at least 5 days, of ≥ 50,000/µL AND an increase of platelet count of ≥ 20,000/µL from baseline, by dose level, without use of rescue medication in the 4 weeks prior to the latest elevated platelet count.

4.2 Secondary Efficacy Endpoints

The secondary efficacy endpoints are:

- 1) Percent of weeks with platelet counts \geq 50,000/ μ L by dose level and overall
- 2) Proportion of patients with 4 out of the final 8 platelet counts \geq 50,000/ μ L across all dose levels
- 3) Change from baseline to the average of the post Day 1 platelet counts by dose level and overall for patients had > 4 weeks of study drug on that given dose level
- 4) Number of weeks with platelet counts ≥ 50,000/μL across all dose levels
- 5) Number of weeks with platelet counts ≥ 30,000/μL across all dose levels
- 6) Time to first platelet count ≥ 50,000/μL across all dose levels

4.3 Exploratory Measures

4.4 Pharmacokinetic Outcome Measures

Plasma pharmacokinetic (PK) parameters (C_{max} , T_{max} , AUC, $t_{1/2}$, V/F, CL/F) of rilzabrutinib in ITP patients will be evaluated in each patient based on frequent sampling on Day 1 of a new, higher dosing level and

reported by dose and, if relevant, overall. Exploratory analyses will pool these data with the data from other studies of rilzabrutinib.

4.5 Changes to Planned Analyses from the protocol

Change	Description	See SAP section
Analysis populations	The Screening and ITT Exposed population defined in protocol sections 10.7.1 and 10.7.3 were replaced by:	3.2
	Intent-to-Treat (ITT) population	
	All summarises of baseline characteristics and efficacy analyses will be done in the ITT population.	
Secondary endpoints	The following secondary endpoints defined in protocol section 10.3 are replaced:	4.2
	 Proportion of patients able to achieve two or more platelet counts of ≥ 50,000/μL AND increase of platelet count of ≥ 20,000/μL from baseline at any time (on treatment or during follow up) without use of rescue medication in the 4 weeks prior to the latest elevated platelet count Proportion of patients able to achieve two or more platelet counts, separated by at least 5 days, representing an increase of platelet count of ≥ 20,000/μL from baseline, by dose level, without use of rescue medication in the 4 weeks prior to the latest elevated platelet count Proportion of patients able to achieve two or more platelet counts, separated by at least 5 days, of ≥ 100,000/μL, by dose level, without use of rescue medication in the 4 weeks prior to the latest elevated platelet count Change from baseline to the average of the last two platelet counts at each dosing level Time to first platelet response (as defined in the primary endpoint) Proportion of patients that completed 24 weeks of treatment and demonstrated a platelet response defined as platelet counts ≥ 50,000/μL at ≥ 50% of the visits during the last 8 weeks of the active treatment period 	
	With the following secondary endpoints:	
	 Percent of weeks with platelet counts ≥ 50,000/µL by dose level and overall 	

	e SAP
2) Proportion of patients with 4 out of the final 8 platelet counts ≥ 50,000/µL across all dose levels 3) Change from baseline to the average of the post Day 1 platelet counts by dose level and overall for patients had > 4 weeks of study drug on that given dose level 4) Number of weeks with platelet counts ≥ 50,000/µL across all dose levels 5) Number of weeks with platelet counts ≥ 30,000/µL across all dose levels 6) Time to first platelet count ≥ 50,000/µL across all dose levels The following secondary endpoints defined in protocol section 10.3 are defined as safety endpoints in section 5.5: 1) Percentage of participants receiving rescue medication at each dosing level and overall 2) Proportion of patients with a Grade 2 or higher bleeding event at each dosing level and overall 3) Bleeding scale (ITP Bleeding Assessment Tool [ITP-BAT]) at the end of treatment period for each dosing level Additional exploratory endpoints	

Change	Description	See SAP section
Additional efficacy analyses	Subset analysis and predictive platelet count analysis are added for the primary efficacy endpoint.	5.4.1.1 and 5.4.1.2
Additional safety endpoints	The following new safety endpoints were defined as secondary efficacy endpoints in the protocol:	5.5
	 4) Percentage of participants receiving rescue medication at each dosing level and overall 5) Proportion of patients with a Grade 2 or higher bleeding event at each dosing level and overall 6) Bleeding scale (ITP Bleeding Assessment Tool [ITP-BAT]) at the end of treatment period for each dosing level 	

5 ANALYSIS DETAILS

All study visits including the LTE visits will be included for the patient disposition tables and listings when applicable. Data collected during the LTE period will be summarized for the efficacy and safety analyses as needed.

5.1 Patient Disposition, Demographics and Baseline Characteristics

The ITT population will be used for patient disposition, demographics and baseline characteristics. Descriptive statistics will be done by starting dose and overall, unless specified otherwise. Patient data listings will be listed by starting dose, patient ID and start date of event, if applicable.

5.1.1 Patient Disposition

The number and percentage of patients will be tabulated for patients who:

- Enrolled into the study
- Received at least one dose of study drug
- Completed the main study
 - o Completed 24 weeks of treatment (defined in section 3.4.11)
- Entered into LTE
 - o Ongoing in LTE
 - Withdraw from LTE
 - Primary reason for withdrawal
- Did not enter into the LTE period
- Early withdraw from main study
 - Primary reason for early discontinuation

The number of percentages of patients enrolled by country and study site will also be tabulated. Frequency table will also be created for the number and percentage of patients in each analysis populations.

Disposition information will be listed by starting dose.

Reason for Screen failures will be summarized.

5.1.2 Demographics and Baseline Characteristics

Demographics variables including age, age group (< 65 and >= 65 years; interquartile range), gender, method of birth control for female patients, race, ethnicity, height at screening, weight at screening and body mass index (BMI) at screening will be summarized by descriptive statistics.

5.1.3 ITP History

ITP history data including type of ITP (primary or secondary), duration of ITP (primary or secondary) (years), average of the most recent and second most recent screening platelet count, baseline platelet count, time since the most recent prior therapy resulted in a platelet response (months), splenectomy done (Y/N), time since splenectomy (months), number of prior ITP therapies, number of prior corticosteroids ITP therapies, number of prior TPO-RAS ITP therapies, number of other ITP therapies, and the last treatment that the patient responded to will be summarized and listed.

The number of prior ITP therapies is based on the record identifier of ITP medications. Splenectomy will be counted as one prior ITP therapy.

